14.0 Statistical Methods

This clinical trial includes a phase I dose-finding study and a phase II efficacy study. The phase I portion requires up to 18 patients. The phase II portion needs an additional 24 patients (6 carried over from phase I using the RP2D level) for a study total of up to 42 patients and a phase II total of 30 patients. With 2 centers, each accruing 1-2 patients per month, we anticipate completing enrollment in 18 months.

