14.1. Phase I Portion of the Study

14.1.1. Study Design

The primary objectives of the phase I portion are to determine the maximum tolerated dose (MTD) of duvelisib when combined with anti-PD1 therapy nivolumab, and to decide on its recommended phase II dose (RP2D). Dose escalation will follow the decision rule in the following table, using the three dose levels defined in Section 7.5 (i.e., 15mg Daily, 25mg Daily, and 25mg BID), starting from the lowest dose. The MTD is defined to be the highest dose level at which no more than 1 of 6 treated patients experiences a DLT (DLT is defined in Section 8.1). Cohorts of three to six patients each will be treated at a dose level. Patients should have taken 75% of pills to be included in analysis of their respective cohort, as assessed through pill counts and pill diary. Only toxicities observed during the first treatment cycle will affect dose escalation. Late toxicities observed will be discussed at monthly data safety monitoring boards to determine if dose adjustments should be made.

After MTD is determined, we will decide on RP2D based on an overall consideration of DLT data, as well as immune cell profiling with laboratory correlates. For this purpose, our decision rule in the following table is a slight modification of the standard “3+3” to make sure 6 patients will be accrued at each safe dose in order to have enough patients for laboratory evaluations. RP2D should not be higher than MTD. If the MTD is not reached, RP2D will be decided based on safety data from acute and late toxicities as well as immune cell profiling data by the investigators (see section 13.1).

DECISION RULES FOR DOSE LEVEL ESCALATION

No. of patients with DLT's at this dose level	No. of patients treated at this dose level	Action
≤1	3	Treat 3 more patients at this dose level.
≤1	6	Treat 3 patients at the next higher dose level (or if at the highest level, stop the trial, and declare the dose at this level to be the MTD).

>1	3 or 6	Stop dose escalation. The previous dose is defined as MTD.
----	--------	--

Cohorts need not be completed if clear decisions can be made on the basis of an incomplete cohort. For example, if the first two patients in an intended cohort of three experience DLT's, escalation can be stopped without accruing the third member of the cohort.

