14.2.3.3. Stopping Rule for Excessive Toxicity

We will use a Bayesian monitoring scheme to continuously monitor the dose limiting toxicity rate of the study combination at 30%. The DLT is defined generally as grade 3 and 4 toxicity, see section 8.1 for more detailed definitions. Again, a non-informative prior of Beta (0.5, 0.5) for the DLT rate will be used. We will hold patient recruitment if the posterior probability $\text{Pr}(\text{SAE rate} > 30\%) \leq 0.7$, and the study committee and the PI will then decide whether to modify or discontinue the study. The stopping boundary for toxicity is given in the following table:

Number of SAEs \geq	in Number of Patients =
2	3-5
3	6-7
4	8-10
5	11-13
6	14-16
7	17-19
8	20-22
9	23-26
10	27-29
11	30

We simulate the operating characteristics under various assumed true toxicity rates (see the following table):

Scenario	Prob.Of.Tox	Prob.Early.Stop
1	0.1	0.0885
2	0.2	0.3332
3	0.3	0.6727
4	0.4	0.9128

14.2.3.4. Analysis of Safety (for both the phase I portion and the phase II portion)

We will consider a toxicity event to be an adverse event (evaluated by CTCAE 5.0) that is possibly, probably, or definitely related to treatment. Toxicity will be considered attributable to both study drugs, unless investigator determines one of the drugs is a more likely culprit (e.g. CMV due duvelisib). The maximum grade of toxicity for each category of interest will be recorded for each patient and the summary results will be tabulated by category and grade. These will also be done for early toxicities (within 4 weeks) and late toxicities (after 4 weeks) separately.

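### The early-stop probabilities printed for the phase II toxicity rule are those of 30 new patients, but phase II has 24 new patients plus 6 carried over from a dose level that passed with at most 1 DLT in 6

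*Combined protocol and SAP*

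**What the plan says.** Section 14.0 states that phase II "needs an additional 24 patients (6 carried over from phase I using the RP2D level"), which gives "a phase II total of 30 patients".

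Section 14.1.1 sets the phase I criterion: "The MTD is defined to be the highest dose level at which no more than 1 of 6 treated patients experiences a DLT". It adds that "RP2D should not be higher than MTD", and that the 3+3 scheme was modified "to make sure 6 patients will be accrued at each safe dose". Only first-cycle toxicity drives escalation.

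Section 14.2.3.3 undertakes to "continuously monitor the dose limiting toxicity rate of the study combination at 30" percent, with a Beta(0.5, 0.5) prior and section 8.1 as the source of the DLT definition. Its boundary table runs from n=3 to n=30. It then says "We simulate the operating characteristics under various assumed true toxicity rates (see the following table"), and the Prob.Early.Stop column of that table gives 0.0885, 0.3332, 0.6727 and 0.9128 at true rates 0.1, 0.2, 0.3 and 0.4. The section does not mention the carried-over patients. It speaks of DLTs in the prose but of SAEs in the posterior formula and in the header of the boundary table.

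**The concern.** The boundary table ends at the phase II total of 30, a number the plan reaches only by including the 6 phase I patients. Because the RP2D cannot lie above the MTD, those 6 come from a level that passed with at most 1 DLT in 6. A group selected in that way cannot cross the early boundaries (2 events at n=3 to 5, 3 events at n=6), yet those looks supply most of the printed stopping probability at rates of 10 to 40%.

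This is the only phase II toxicity rule for which the plan gives operating characteristics. Once the RP2D is fixed, the 24 new patients rely on it. A monitoring board reading the column would expect a pause with probability 0.91 at a true DLT rate of 40%. On the reading that the 6 count, it would be 0.67.

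**Working it through.** **Inputs.** The boundaries are from section 14.2.3.3: at least 2 events in 3–5 patients, 3 in 6–7, 4 in 8–10, 5 in 11–13, 6 in 14–16, 7 in 17–19, 8 in 20–22, 9 in 23–26, 10 in 27–29, 11 in 30. The 24 + 6 composition is from section 14.0. The limit of 1 DLT in 6 and the cap of the RP2D at the MTD are from section 14.1.1. The DLT window, first combination dose to day 28, is from section 8.1.

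**Boundary check.** With a Beta(0.5, 0.5) prior, the smallest count giving Pr(rate > 30%) > 0.7 regenerates every printed boundary from n=3 to n=30. (The text prints the inequality as ≤ 0.7; the table corresponds to > 0.7.)

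**Method.** Exact recursion on the cumulative event count s. After each patient, P(n, s) = (1−p)·P(n−1, s) + p·P(n−1, s−1). All mass at or above the boundary is removed and added to the stopping probability.

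**Step 1: reproduce the plan.** Starting from 0 events in 0 patients, with 30 patients and a look at every n from 3, the result is 0.0885 / 0.3332 / 0.6727 / 0.9128. This matches the printed column to four decimals. Looks every 5 patients (0.0850 / 0.3076 / 0.6269 / 0.8864), looks every 3 patients (0.0398 / 0.2128 / 0.5517 / 0.8597) and a first look at n=6 (0.0318 / 0.2302 / 0.6024 / 0.8914) do not match.

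**Step 2: where the printed probability arises.** In 30 new patients the boundary is crossed by n=6 with probability 0.0815 / 0.2627 / 0.4718 / 0.6630.

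**Step 3: earliest crossing with the 6 counted.** Start from at most 1 event at n=6. At n=7 the count is at most 2 (boundary 3), at n=8 at most 3 (boundary 4), and at n=9 at most 4 (boundary 4). So n=9 is the first possible crossing.

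**Step 4: conditional stopping probability.** The chance of passing phase I at a level is (1−p)^6 + 6p(1−p)^5. The starting weights at n=6 are the two terms divided by their sum. At p=0.3 they are 0.1176 and 0.3025, with sum 0.4202. The recursion from 0/6 gives 0.1726 and from 1/6 gives 0.3560, so the stopping probability is (0.1176×0.1726 + 0.3025×0.3560)/0.4202 = 0.305.

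**Step 5: whole path.** P(stopped at either stage) = 1 − P(pass)·(1 − conditional stop). At p=0.4 this is 1 − 0.2333×(1 − 0.6719) = 0.923.

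**Step 6: alternative.** The same boundaries applied from zero to the 24 new patients only.

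| True rate | Printed | Pass phase I | 6 counted, conditional | Phase I and II together | 24 new only |
|---|---|---|---|---|---|
| 10% | 0.0885 | 0.8857 | 0.003 | 0.117 | 0.088 |
| 20% | 0.3332 | 0.6554 | 0.061 | 0.385 | 0.326 |
| 30% | 0.6727 | 0.4202 | 0.305 | 0.708 | 0.640 |
| 40% | 0.9128 | 0.2333 | 0.672 | 0.923 | 0.879 |

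**Step 7: sensitivity to the event.** Suppose later events also count. Assume that 25 to 75% of events fall by day 28, that the row's rate is the total event rate, and that the 6 are first checked at n=6. The stopping probability is then 0.58 down to 0.43 at 30%, and 0.88 down to 0.78 at 40%. The split is an assumption; the documents give no such fraction.

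**The case against.** Four objections deserve weight.

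*The plan never says the 6 count toward toxicity.* That is correct. The carry-over appears in the sample-size paragraph of section 14.0, and a boundary printed to n=30 is suggestive, not conclusive. If only the 24 new patients count, the true figures are within 0.034 of those printed. What stands on either reading is that the column is not this design's, because no phase II group consists of 30 new patients. The gap is large only if the 6 count.

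*The event is not settled.* The cap of 1 event requires the day-28 DLT. The prose of section 14.2.3.3 and the continuous DLT monitoring in section 3.2.2 favour that reading. The formula, the table header and the synopsis point to SAEs or severe adverse events. Section 8.2.2 collects SAEs to 100 days after the last dose, and sections 11.1 to 11.4 give median onsets of 3 to 4 months for the main duvelisib toxicities. Under that reading the carried-over patients could contribute more than 1 event. The shortfall narrows, but in the illustration above it does not vanish.

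*Phase I already does the early stopping.* A reader might infer that the trial as a whole protects far less than stated, or that a 40%-toxic dose escapes 33% of the time instead of 9%. The documents do not support that. The 33% applies only to a dose that has already passed phase I, which a 40% dose does with probability 0.23. Over the whole path such a dose escapes with probability 0.2333×0.3281 = 0.077, against 0.087 implied by the printed table.

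*No sum is wrong, and a crossing is not final.* Both are true. The printed values are right for the printed boundaries; the fault is the unstated assumption of 30 new patients. A crossing holds recruitment for a decision by the study committee and the PI. Monthly review covers late toxicities, and section 10.1 lets the DSMB and DSMC suspend accrual. This lowers the severity but does not make the column correct.

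**Conclusion.** The point holds in a limited form. The Prob.Early.Stop column describes 30 new patients, which phase II does not have. If the 6 carried-over patients count and the event is the day-28 DLT, the chance that the phase II rule pauses recruitment is 0.305 instead of 0.673 at a true rate of 30%, and 0.672 instead of 0.913 at 40%. At 10% and 20% the lower figures mean fewer unnecessary pauses.

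The loss concerns the 24 new patients once the RP2D is chosen, not the combined phase I and II screening, which is slightly above the printed column in every row. The result assumes independent patients with a constant event rate and exactly 6 carried over. Should-fix.

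**What to change.** In section 14.2.3.3:

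1. Use one event throughout. If it is the section 8.1 DLT, replace SAE in the posterior formula and the boundary-table header.
2. State which patients enter the count.
3. Replace the Prob.Early.Stop column to match, in one of two ways:
   - **(a)** Count the 6. Print the conditional figures (0.003 / 0.061 / 0.305 / 0.672) beside the whole-path figures (0.117 / 0.385 / 0.708 / 0.923), each labelled for what it is.
   - **(b)** Start the count at zero for the 24 new patients, keep the same boundaries through n=24, and print 0.088 / 0.326 / 0.640 / 0.879.

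If events after day 28 are to count, the conditional and whole-path figures in (a) do not apply and must be simulated again with a stated event window.

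Neither option adds patients; the change is to wording and one table. The cost of (a) is that the stated protection of the new patients becomes visibly lower. The cost of (b) is that the rule ignores 6 patients' data at the same dose. Its chance of a pause at a 10% rate stays at about 9%, which the plan already accepts.

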14.2.3.5. Analysis of exploratory endpoints

The effect of duvelisib dose on marker expression will be exploratively analyzed with generalized linear models, where baseline marker value, duvelisib dose and measurement time are explanatory variables. Also, pre- and post- treatment marker expression values will be compared with paired t-tests or Wilcoxon signed rank tests as appropriate.

15.0 Study Management, Agreement and Ethical Considerations

This study will be managed in the UPMC Melanoma Center which has considerable experience in managing clinical trials. Screening, registration, safety and efficacy evaluations are described in detail above. The study funding will come predominantly from Secura Bio, Inc the manufacturer of duvelisib. Study design, operations and procedures were designed independently by the co-investigators and were compliantly reviewed by appropriate experts on the Secura Bio clinical/scientific team.

Without a standard of care option for anti-PD1 refractory disease, clinical trials are a preferred treatment according to NCCN guidelines ¹. Our trial is a reasonable option for patients who have progressed on anti-PD1 therapy and who have exhausted BRAF targeted therapy, which is ultimately the majority of patients with advanced melanoma. Toxicities with duvelisib were observed in heavily pre-treated patients with hematologic malignancies ¹². Patients with melanoma are less immuno- and myeloid suppressed and should tolerate duvelisib with fewer toxicities. Studies with duvelisib in other solid tumors are also being planned.

17.0 Appendices

17.1 Appendix A: Medications with CYP3A interactions

Table 17.1 Inhibitors and Inducers of CYP3A

Potent CYP3A Inhibitors	
Antibiotics or antifungals	Clarithromycin, erythromycin, telithromycin
Anti-emetic	Aprepitant
Antifungals	Itraconazole, ketoconazole, voriconazole, posaconazole
Antiretrovirals	Ritonavir, idinavir, nelfinavir, boceprevir, cobicistat, elvitegravir, paritaprevir, telaprevir, tipranavir
Calcium channel inhibitors	Diltiazem, verapamil
Foods	Grapefruit juice
Antidepressant	Nefazodone
Tyrosine Kinase Inhibitor	Imatinib
Potent CYP3A Inducers	
Anti-epileptics	Carbamazepine, phenobarbital, phenytoin
Antibiotics	Rifampin
Antiretrovirals	Efavirenz, etravirine
Supplements	St John's wort
CYP3A Sensitive Substrates	
Analgesic/Benzodiazapine	Alfentanil, midazolam, naloxegol, triazolam,
Aldosterone receptor antagonist	eplerenone
Anti-arrhythmic	dronedarone
Anticholinergic	darifenacin
Antihistamine	ebastine
Anti-retroviral	Darunavir, indinavir, maraviroc, saquinavir, tipranavir,
Antidepressant/antipsychotic	Buspirone, lurasidone, quetiapine
Calcinineurin / mTor inhibitors	Everolimus, sirolimus, tacrolimus
Calcium channel blockers	Nisoldipine, felodipine
CONTINUED...	

Platelet aggregation inhibitor	ticagrelor
Phosphodiesterase inhibitor	avanafil, sildenafil, vardenafil
Statin/lipid lowering agents	Lomitapide, lovastatin, simvastatin
Steroid	Budesonide
Triptan	Eletriptan
Tyrosine kinase inhibitor	dasatinib, ibrutinib
Vaptans	Conivaptan, tolvaptan

References: ^{26, 27},

17.2 Appendix B: Drug Diary

Participant: _____

Your MD _____ Phone _____

Your RN _____ Phone _____

DOSING LOG

Duvelisib Dose ____ Cycle: ____

For each AM dose take: 1 pill

For each PM dose take: 1 pill

	Date	Amount Taken		Comments
		AM dose	PM dose	
Ex:	6/1/2019	8 am - 1	7:30 pm - 1	vomited PM pill
Day 1				
Day 2				
Day 3				
Day 4				
Day 5				
Day 6				
Day 7				
Day 8				
Day 9				
Day 10				
Day 11				
Day 12				
Day 13				
Day 14				

Day 15				
Day 16				
Day 17				
Day 18				
Day 19				
Day 20				
Day 21				
Day 22				
Day 23				
Day 24				
Day 25				
Day 26				
Day 27				
Day 28				

Please bring any unused study drug, all empty containers, and your diary to the next clinic visit

FOR STUDY TEAM USE ONLY	
Staff Initials:	
Date Dispensed:	Date Returned:
# pills/caps/tabs dispensed:	# pills/caps/tabs returned:
# pills/caps/tabs that should have been taken:	
Discrepancy Notes:	

SUMMARY OF CHANGES

Protocol dated 4-27-22

Page 1	Version date changed from 3-11-22 to 4-27-22
Page 1 - 2	Removed references to Emory University
Page 8	Table ii. Protocol Summary, Methodology, Removed "multi-center"
Page 8	Table ii. Protocol Summary, Removed reference to Emory Winship Cancer Institute
Page 14	Section 3.1, General Study Design, Removed "multi-center study to be conducted at Winship Cancer Institute at Emory University"
Page 17	Section 4.2, Exclusion Criteria, 1 st bullet, Removed "with"
Page 20	Section 4.3, Subject Recruitment, 1 st sentence, Removed "Emory Winship Cancer Institute"
Page 23	Section 5.4, Procedure for Registration of Subjects, Removed "Winship Cancer Institute of Emory University;"
Page 22	Section 5.1, Study Site, Removed "Winship Cancer Institute"
Page 28	Section 7.4.1, Receipt of Drug Supplies, Removed "Winship Cancer Institute"
Page 30	Table 7.6, Dose Adjustments for Toxicity, Updated recommended management for Neutropenia
Page 37	Section 7.7, Removed references to Emory
